## 4 STUDY DESIGN

### 4.1 OVERALL DESIGN

The hypothesis under study is that one or more applications of TTAX01 to the wound surface of a well debrided, complex diabetic foot ulcer managed with appropriate antibiotic therapy will result in a higher probability of complete healing than would be expected from management with standard care alone. In this open label Phase 2 pilot trial, all subjects will receive the intervention over a maximum period of 16 weeks. Eligible consenting subjects will undergo a baseline aggressive debridement in the operating room to remove infected and devitalized bone and soft tissue. A six week course of systemic antibiotics will be used to resolve baseline infection. TTAX01 will be applied to the debrided wound bed at baseline, and if healing is not evident, it will be applied again at 4 week intervals. At each weekly visit the wound will be further debrided as necessary.

To reduce bias in the ascertainment of complete closure, one independent observer will review the image obtained from a wound measurement device (eKare inSight™) in each case where the Investigator makes a determination of closure. Discordant opinions will be adjudicated by a third independent reviewer who will examine multiple additional images taken at various angles to the wound surface.

Bias will be further controlled by distributing enrollment over approximately twelve clinical sites. Because all subjects will receive the intervention, there will be no stratification on variables known to influence the probability of healing (e.g., wound size, wound duration, gender). No interim analysis is planned, but an ongoing review of protocol compliance may lead to amendments where it is determined that additional clarity is needed. It is expected that operational issues with this protocol will be worked through in anticipation of designing a similar, pivotal Phase 3 trial.

Consenting subjects who qualify for enrollment will undergo an aggressive surgical debridement at the baseline visit, including biopsies of bone for histology and microbiologic testing at the start

and completion of debridement. Systemic antibiotics will be given empirically, with adjustments made on the basis of culture and sensitivity results. New or recurrent infections will be managed with additional debridement and adjustment or addition of appropriate systemic antibiotics. The test article, TTAX01, will be surgically fixed using sutures or staples to the debrided wound bed at baseline and again at 4 week intervals over the 16-week treatment period for wounds that do not show evidence of healing. For wounds that do show evidence of healing, additional applications of TTAX01 will be withheld, based on observations from retrospective case series (refer to Section 2.3.2)

Subjects whose wounds close prior to 16 weeks will move directly to a 2-week confirmation of closure. Subjects whose wounds have not closed by the end of 16 weeks will exit the trial.

## 4.2 SCIENTIFIC RATIONALE FOR STUDY DESIGN

The prospective, multi-center design of this trial should serve to reduce selection and ascertainment bias compared with retrospective case series reported by individual clinicians. The design is expected to yield a more accurate estimate of response rates for the population under study, which can be used for statistical power calculations of a larger controlled trial. The open label design allows the Sponsor to immediately consider the relationship between treatment emergent adverse events and the test article, against the background of anticipated adverse events in this population.

## 4.3 JUSTIFICATION FOR DOSE

## 4.4 END OF STUDY DEFINITION

A subject is considered to have completed the study if he or she has completed the End of Treatment Visit 19, shown in the Schedule of Activities (SoA), Section 1.3.

## 5 STUDY POPULATION

Adult subjects aged  $\geq 18$  year-old with reasonably controlled diabetes mellitus and a complex non-healing DFU with high risk factors of [1] ulcer depth indicating exposed bone, tendon, muscle, and/or joint capsule and [2] clinical suspicion of osteomyelitis will be recruited for this trial. Assuming a screen failure rate of 30%, 47 potential subjects may be screened to enroll 36.

## 5.1 INCLUSION CRITERIA

In order to be eligible to participate in this study, an individual must meet all of the following criteria:

1. The subject has signed the informed consent form
2. The subject is male or female, at least 18 years of age inclusive at the date of Screening
3. The subject has confirmed diagnosis of Type I or Type II diabetes
4. The subject's index ulcer is located on the plantar surface, inter digital, heel, or lateral or medial surface of the foot
5. The subject has an index ulcer with visible margins having an area  $\geq 1.0 \text{ cm}^2$  to  $\leq 10.0 \text{ cm}^2$  when measured by the electronic measuring device at Screening
6. The subject's index ulcer extends beyond the dermis, into subcutaneous tissue with evidence of exposed bone, tendon, muscle and/or joint capsule
7. The subject presents with history, signs or symptoms leading to a clinical suspicion of osteomyelitis in the opinion of the Investigator supported by positive Probe to Bone (PTB) and any of the following: radiographic (x-ray, Magnetic Resonance Imaging (MRI), or bone scan) or evidence of bone necrosis
8. The subject has an ABI  $\geq 0.7$  to  $\leq 1.3$  or TcPO2  $\geq 40 \text{ mmHg}$  on the dorsum of the affected foot, or Great Toe Pressure  $\geq 50 \text{ mmHg}$
9. The subject is under the care of a physician for the management of Diabetes Mellitus
10. The subject is willing to return for all mandatory visits as defined in the protocol
11. The subject is willing to follow the instructions of the trial Investigator

## 5.2 EXCLUSION CRITERIA

An individual who meets any of the following criteria will be excluded from participation in this study:

1. The subject's index ulcer is primarily located on the dorsal surface of the foot
2. The subject's index ulcer can be addressed by primary closure through the completion of the initial or staged surgical procedure
3. The subject has a glycated hemoglobin A1c (HbA1c) level of  $> 12\%$
4. The subject has a serum albumin level  $\leq 2.0 \text{ g/dL}$
5. The subject has a white blood cell count  $< 2.0 \times 10^9/\text{L}$ , neutrophils  $< 1.0 \times 10^9/\text{L}$ , or platelets  $< 100 \times 10^9/\text{L}$
6. The subject has been on oral steroid use of  $> 7.5 \text{ mg}$  daily for greater than seven (7) consecutive days in 30 days before Screening

7. The subject has been on parenteral corticosteroids, or any cytotoxic agents for seven consecutive days in the period of 30 days before Screening
8. The subject is currently taking the type 2 diabetes medicine canagliflozin (Invokana™, Invokamet™, Invokamet XR™)
9. The subject has malignancy or a history of cancer, other than non-melanoma skin cancer, in five years before Screening
10. The subject is pregnant
11. The subject is a nursing mother
12. The subject is a woman of child-bearing potential who is unwilling to avoid pregnancy or use an appropriate form of birth control (adequate birth control methods are defined as: topical, oral, implantable, or injectable contraceptives; spermicide in conjunction with a barrier such as a condom or diaphragm; IUD; or surgical sterilization of partner).
13. The subject is unable to sustain offloading as defined by the protocol
14. The subject has an allergy to primary or secondary dressing materials used in this trial
15. The subject has an allergy to Amphotericin B, Dulbecco's Modified Eagle Medium (DMEM) or glycerol
16. The subject's index ulcer is over an acute Charcot deformity
17. The subject has had previous use of NEOX®, CLARIX®, or TTAX01 applied to the index ulcer
18. Per Investigator's discretion the subject is not appropriate for inclusion in the trial, e.g., undergoing surgical treatments listed in the protocol or the subject currently has sepsis, i.e., life-threatening organ dysfunction caused by a dysregulated host response to infection

### 5.3 LIFESTYLE CONSIDERATIONS

Subjects are expected to maintain ongoing care and management of their diabetes under the supervision of a qualified diabetologist, endocrinologist or internist with appropriate specialty training and experience. The need for offloading of the wound requires compliance with daily wearing of the offloading device, which may limit ambulation to some degree.

### 5.4 SCREEN FAILURES

Screen failures are defined as potential subjects who consent to participate in the trial but are not subsequently entered. Screen failure information will be captured to ensure transparent reporting of screen failure participants, to meet the Consolidated Standards of Reporting Trials (CONSORT) publishing requirements and to respond to queries from regulatory authorities. Minimal information includes demography, screen failure details, eligibility criteria, and any serious adverse event (SAE).

Individuals who do not meet the criteria for participation in this trial because of an abnormal lab test result, wound size out of range, current treatment with an excluded medication or inadequate

perfusion to the ulcerated foot may be rescreened ONE TIME. Rescreened participants will be assigned the same participant number as for the initial screening.

## 5.5 STRATEGIES FOR RECRUITMENT AND RETENTION

Potential study subjects will be recruited primarily from the clinical practice of the participating study sites. Investigators will share with their clinical staff the inclusion and exclusion criteria, which may also be provided by the Sponsor on a laminated card. Any signage or advertising at the clinics relating to this trial will have been previously submitted to and approved by the relevant IRB.

Broader advertising through newspaper, radio, or fliers or posters in adjacent healthcare facilities will only be used if recruitment falls substantially below the expected rate of one screened subject per site per month. All such advertising will have been previously submitted to and approved by the relevant IRB.

Enrolled subjects will receive a nominal stipend to offset travel and meal costs for the duration of their participation. The actual amount will depend upon IRB approval, but in no case will it be intended to create an incentive to ignore the risks associated with participation in the trial. Additional details are found in a separate recruitment and retention plan document.

## 6 STUDY INTERVENTION

### 6.1 STUDY INTERVENTION(S) ADMINISTRATION

#### 6.1.1 STUDY INTERVENTION DESCRIPTION

#### 6.1.2 DOSING AND ADMINISTRATION

TTAX01 will be applied directly to the wound surface and surgically fixed with sutures or staples. A single layer of the test article should cover the entire open surface of the wound. TTAX01 may overlap onto adjacent healthy tissue and must be fenestrated prior to or after fixture. The material is to be applied once every 4 weeks unless the wound shows evidence of healing, in which case product will be withheld; or, if the test article has been accidentally dislodged within 1-week post application, it may be replaced at the subsequent treatment visit. Wounds showing evidence of new or recurrent soft tissue infection must undergo debridement and receive antibiotic therapy

before considering another application of TTAX01. Wounds showing new or recurrent clinical suspicion of osteomyelitis must establish the diagnosis of osteomyelitis and if positive, repeat the Initial Procedure Visit, including reapplication of TTAX01.

## 6.2 PREPARATION/HANDLING/STORAGE/ACCOUNTABILITY

### 6.2.1 ACQUISITION AND ACCOUNTABILITY

The Investigator shall be responsible for ensuring the records adequately document the disposition of all TTAX01 received by the site for the trial. Documentation includes review of shipment papers to confirm accurate receipt, and disposition of all product received by site. Any product used on a trial subject should be documented both in the subject record and on the product accountability log. Any unused product and/or product past expiration will be returned to the Sponsor following product accountability completed by the Sponsor.

Participation by a pharmacy or drug repository unit is not mandated, however, the test article must be maintained in a secured (locked) environment with limited access to ensure accountability.

### 6.2.2 FORMULATION, APPEARANCE, PACKAGING, AND LABELING

#### 6.2.3 PRODUCT STORAGE AND STABILITY

#### 6.2.4 PREPARATION

Handling Instructions for the test article are as follows:

1. If frozen, allow TTAX01 to sit at controlled room temperature in its original unopened packaging for at least 5 minutes.
2. Open the outer foil peel pouch and present the clear inner peel pouch to the sterile field using aseptic techniques.
3. Open the inner clear peel pouch to retrieve the TTAX01.
4. Secure the TTAX01 on the wound bed.

### 6.3 MEASURES TO MINIMIZE BIAS

The trial is open label, with no blinding of the site staff. All eligible subjects will be enrolled into a single active treatment arm. The determination of wound closure will be made by the Investigator based on visual and tactile assessment of the wound. High quality photographic images will be taken at each visit, from an angle and distance recommended for optimum computerized calculation of wound area. In the event that the Investigator determines that a wound is completely healed, several additional images will be acquired at different angles in order to observe surface reflection of light from newly formed epithelium, and the absence of exudate. An independent reviewer will examine the first photographic image in order to make a determination of wound closure. If this opinion is concordant with the Investigator's opinion, the wound will be recorded as healed. If the independent reviewer finds reason to disagree with the Investigator, a third independent reviewer will examine all of the photographs for the purpose of breaking the tie.

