Subjects' identified index ulcer will be assessed over the course of the treatment visits (Visit BS and Visits 1 through 16) or until their ulcers close. Subjects whose ulcers have closed, as assessed by the investigator and verified by an independent blinded evaluator using the images collected via the electronic wound imaging and measurement device, prior to the 16th week of treatment (or Visit 15) will stop treatment and return for two consecutive weekly visits (i.e., Visits 17, and 18) to verify if the target ulcer remains closed at these two visits following the initial observation of ulcer closure, which is defined as the complete ulcer closure in this study. Two weeks after the 2nd confirmatory visit (Visit 18), subjects with index ulcer remained as closed at Visits 17 and 18 will return and complete an End of Treatment Period visit (Visit 19). Subjects whose ulcers have not closed at the end of the 16-week treatment (i.e., Visit 16) or whose ulcers have re-opened during the confirmatory visits (Visits 17 and 18) will move on directly to complete the assessments of Visit 19. Visit 19 will serve as the study's End of Treatment (EOT) visit for the treatment and ulcer closure confirmatory period and will also serve as study exit visit.

For those subjects who are enrolled and discontinue from the treatment prior to Visit 16 due to any reasons other than target ulcer closure, Visit 19 will serve as the early termination (ET) visit.

The total duration of study starting from enrollment to the end of the treatment period is 16 weeks, during which time adverse events and ulcer-related complications, including limb amputation are assessed.

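### The first independent closure reviewer sees one image only, so a wrong agreement is never tested against the multi-angle images already taken at that visit

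*Protocol*

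**What the plan says.** Protocol 6.3 leaves the closure decision to the Investigator, by sight and touch. A photograph framed for area calculation is taken at every visit. Once closure is called, a further step applies: "additional images will be acquired at different angles in order to observe surface reflection of light from newly formed epithelium, and the absence of exudate".

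The independent check is then: "An independent reviewer will examine the first photographic image in order to make a determination of wound closure". On agreement: "If this opinion is concordant with the Investigator's opinion, the wound will be recorded as healed". On disagreement, "a third independent reviewer will examine all of the photographs for the purpose of breaking the tie".

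Protocol 4.1 describes the same two tiers: "one independent observer will review the image obtained from a wound measurement device (eKare inSight™) in each case", with discordant cases going to "a third independent reviewer who will examine multiple additional images taken at various angles to the wound surface". Read together, 6.3 and 4.1 indicate that the first image is the area-measurement image.

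SAP 2.2 words the check differently. There, closure is "verified by an independent blinded evaluator using the images collected via the electronic wound imaging and measurement device", which uses the plural and adds blinding.

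What follows a closure call also matters:
- Protocol 3 requires the closure to be confirmed at later visits over four weeks, and SAP 2.2 defines complete closure as the ulcer staying closed at Visits 17 and 18.
- Under Protocol 8.1.5 and SAP 2.2, a wound found open at Visit 17 or 18 goes to Visit 19.
- Under Protocol 8.2, a subject whose wound the independent reviewers judge unhealed goes back to the regular treatment visits.

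**The concern.** The endpoint in Protocol 3 turns on full epithelial cover and no drainage. By the protocol's own account the extra-angle images are taken to show those features. They exist at every closure call, yet the person verifying the call does not see them unless that person has already disagreed.

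The trial is open label with one arm, and the Investigator is unblinded, so the independent read is an important safeguard against optimistic calls. Its estimate also matters beyond this pilot: Protocol 4.2 intends the response rate to feed power calculations for a larger controlled trial. The quantities at stake are the primary healing proportion, time to closure and the week-by-week closure proportions.

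**Working it through.** The plan states no figure on this point, so there is none to reproduce. The check is a reading of the rules followed by a scale calculation.

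**Step 1. The four possible outcomes at a closure call (Protocol 6.3)**

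| True state | First reviewer | What happens | Full image set used? |
|---|---|---|---|
| Closed | Agrees | Recorded as healed, correctly | Not needed |
| Closed | Disagrees | Third reviewer decides | Yes, error can be corrected |
| Open | Disagrees | Third reviewer decides | Yes |
| Open | Agrees | Recorded as healed, wrongly | No |

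The gap is in the last row. It does not depend on whether a single image makes agreement more or less likely.

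**Step 2. Where a last-row case goes next**

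- *The wound closes before Visit 17 and stays closed.* Protocol 3 dates time to closure from the first observation, so the recorded date is early. If Visit 17 would detect an open wound, the error is at most about one visit interval (7 ± 2 days). Weekly closure proportions may be shifted in the same way. If the call was made at Visit 16, the subject can also count as healed within 16 weeks without having been so. Primary proportion: unchanged or up.
- *The wound is open but is judged closed again at Visits 17 and 18.* Primary proportion: up.
- *The wound is found open at Visit 17 or 18.* The subject goes to Visit 19, and the readable text describes no return to the treatment visits. A subject who might have healed later becomes a failure. Primary proportion: down.

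**Step 3. Scale**

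The sample size of 36 is from the Protocol synopsis. One subject is 1/36 = 2.8 points. For example, 18/36 = 50.0% (exact 95% CI 32.9 to 67.1) becomes 19/36 = 52.8% (35.5 to 69.6).

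The remaining inputs are assumptions, since the documents give none:
- k, premature Investigator calls: 2 to 6
- m, share of these agreed on one image: 20% to 80%
- c, share of those still wrongly counted as healed after Visits 17 and 18: 0% to 30%

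False closures at the first call = k × m:
- low: 2 × 0.20 = 0.4, and 0.4/36 = 1.1 points
- high: 6 × 0.80 = 4.8, and 4.8/36 = 13.3 points

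False closures left in the primary endpoint = k × m × c:
- low: 0.4 × 0 = 0, or 0 points
- high: 4.8 × 0.30 = 1.44, and 1.44/36 = 4.0 points

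The 0 to 4.0 points are the upward part only. The downward part would need the share of prematurely called subjects who would have healed by week 16 had they stayed in the treatment visits. The documents do not give that share, so I have not put a figure on it.

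**The case against.** The strongest reply is that the first call is only provisional. Protocol 3, Protocol 8.1.5 and SAP 2.2 require the wound to be seen closed again at Visits 17 and 18, so a false agreement is re-examined in person at least twice. This stands for the primary proportion, and it is why the surviving effect is small. It does not repair the closure date, because those visits test whether the wound is closed later, not whether it was closed when called.

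A second reply is that one image need not raise agreement: a doubtful reviewer can disagree and so trigger the full review. That also stands, and the point does not rest on a higher agreement rate. It rests on wrong agreements having no route to the better images.

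A third reply is that a single-image read with full-set adjudication is a legitimate tiered design for a descriptive pilot. It is a choice rather than an error, but a tiered read usually saves effort, and here the extra images are already in hand.

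Three stronger readings are tempting, and the documents do not support them:
- *Agreement makes a premature closure final.* It ends image review of that call, not ascertainment of the primary endpoint.
- *The healing proportion is biased upward.* A premature call found open at Visit 17 or 18 works in the opposite direction, and the net sign is undetermined.
- *Images are never reviewed again.* The visit procedure lists in Protocol 8.1.3 to 8.1.5 and the SAP text on the primary measure and analysis (2.6.1, 2.9.1) are missing or blacked out. Whether image review is repeated at Visits 17 to 19 cannot be determined.

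**Conclusion.** The point holds as a one-sided check at the first closure call: agreement on one image starts the confirmatory path without use of the images best suited to show the endpoint.

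The consequence for the primary proportion is modest. Wrongly retained closures add about 0 to 4 points on the assumed rates above, with an offset of unknown size from subjects taken out of the treatment visits too early. The exact interval at 18/36 is about 34 points wide, so this is a matter of avoidable misclassification and does not by itself overturn the estimate. Time to closure is more directly exposed: a premature call that is later confirmed carries an early date. The weekly proportions may share that error.

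The 0 to 4 points describe wrong agreements that survive. They are not the gain from the fix, which depends on how much better the full image set discriminates, and the documents are silent on that. SAP 2.2 either intends more than one image or conflicts with Protocol 6.3, so the wording needs attention in any case.

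**What to change.** In Protocol 6.3 and 4.1, state that the first independent reviewer receives all images acquired at the visit where closure is called, including the extra-angle set. Keep the third reviewer, on the same set, for disagreements.

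Reconcile this with SAP 2.2, so that both documents name the same image set and agree on whether the evaluator is blinded, and to what.

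The cost is protocol, SAP and reviewer-instruction wording. The reviewer is the same, and the images are already taken. The downside is a few more images to read per called closure and possibly slightly more discordant cases for the third reviewer.
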